6.3 Expectedness

Unexpected adverse event: An adverse event, which varies in nature, intensity or frequency from information on the investigational drug/agent provided in the Investigator's Brochure, package insert or safety reports. Any adverse event that is not included in the informed consent is considered "unexpected".

Expected (known) adverse event: An adverse event, which has been reported in the Investigator's Brochure. An adverse event is considered "expected", only if it is included in the informed consent document as a risk.

6.4 Handling of Expedited Safety Reports

In accordance with local regulations, the IND Sponsor will notify investigators of all SAEs that are unexpected (i.e. not previously described in the Investigator Brochure), and definitely, probably, or possibly related to nivolumab, BMS-813160 or GVAX. This notification will be in the form of an expedited safety report (ESR) that is to be faxed to the investigators and the study coordinators within 48 hours. Upon receiving such notices, the investigator must review and retain the notice with the Investigator's Brochure and where required by local regulations, the investigator will submit the ESR to the appropriate IRB. The investigator and IRB will determine if the informed consent requires revision. The investigator should also comply with the IRB procedures for reporting any other safety information.

6.5 Reporting

6.5.1 General

All adverse events (both expected and unexpected) will be captured on the appropriate study-specific Case Report Forms (CRFs), with the exception of unrelated adverse events that occur during the standard of care treatment periods. The standard of care treatment periods include FOLFIRINOX-based chemotherapy administration and SBRT treatment through initiation of Cycle 1 of combination immunotherapy and from surgical resection or Nanoknife procedure through initiation of Cycle 2 combination immunotherapy. All AEs collected will be reported in aggregate in the final study report, which must be provided to BMS. No individual or expedited reporting is required.

All serious adverse events, regardless of causality to study drug, including those thought to be associated with protocol-specified procedures will be reported promptly to the IND Sponsor and BMS Worldwide Safety within 24 hours of recognition, with the exception of unrelated SAEs that occur during the standard of care treatment periods as defined above. Serious adverse events should be reported using the form found in **Appendix B**. If this falls on a weekend or holiday, an email notification is acceptable but must be followed by an SAE reporting form on the next business day.

SAE reports and any other relevant safety information are to be sent to:

IND Sponsor ([name]): [REDACTED]

BMS: [REDACTED]

After the initial AE or SAE report, the investigator is required to proactively follow each subject and provide further information to the safety department in regard to the subject's condition.

All AE(s) and SAE(s) will be followed until:

- Resolution

A Phase I/II trial of combination immunotherapy with nivolumab and a CCR2/CCR5 dual antagonist (BMS-813160) with or without GVAX following chemotherapy and radiotherapy for locally advanced pancreatic ductal adenocarcinomas (PDACs)

- The condition stabilizes
- The event is otherwise explained
- The subject is lost to follow-up
- Death

As soon as relevant information is available, a follow-up SAE report will be submitted to the IND Sponsor and BMS.

If it is discovered a patient is lactating, pregnant, or may have been pregnant at the time of exposure to the BMS product associated with this study (i.e. from start of study immunotherapy treatment to 5 months after study drug discontinuation), the pregnancy, AEs associated with maternal exposure, and pregnancy outcomes must be reported to the IND Sponsor and BMS within 24 hours on the approved site SAE form. If only limited information is initially available, follow up reports may be required. The original forms will remain on site. Follow-up information should be obtained on pregnancy outcomes for one year following the birth of the offspring.

Any pregnancy or lactation that occurs in a female partner of a male study participant, who has provided written consent to provide information regarding the pregnancy, that occurs during the trial to 7 months after study drug discontinuation should be reported to the IND Sponsor and BMS. Pregnancies must be reported and submitted to the IND Sponsor and BMS on a BMS Pregnancy Surveillance Form or the MedWatch, CIOMS, or approved site SAE form.

All subjects who become pregnant must be followed to the completion/termination of the pregnancy. Pregnancy outcomes of spontaneous abortion, missed abortion, benign hydatidiform mole, blighted ovum, fetal death, intrauterine death, miscarriage and stillbirth must be reported as serious events. If the pregnancy continues to term, the outcome (health of infant) must also be reported to the IND Sponsor and BMS Worldwide Safety.

The Principal Investigator (or designee) will reconcile the clinical database SAE cases (case level only) transmitted to the IND Sponsor and BMS Global Pharmacovigilance (██████████). Frequency of reconciliation should be approximately every 3 months and prior to the database lock or final data summary. BMS GPV&E will email, upon request from the Investigator (or designee), the reconciliation report. Requests for reconciliation should be sent to ██████████. The data elements listed on the BMS GPV&E reconciliation report will be used for case identification purposes. If the Sponsor determines a case was not transmitted to the IND Sponsor and BMS GPV&E, the case should be sent immediately to the IND Sponsor and BMS.

Adverse events that are routinely collected according to GCP shall be submitted to BMS every three (3) months by the last working day of the third month. The adverse event information required to be sent to BMS is noted in an attached 'Bristol-Myers Squibb

A Phase I/II trial of combination immunotherapy with nivolumab and a CCR2/CCR5 dual antagonist (BMS-813160) with or without GVAX following chemotherapy and radiotherapy for locally advanced pancreatic ductal adenocarcinomas (PDACs)

Early Asset Investigator Sponsored Research (ISR) Import Plan' which describes the method of collection and submission to BMS via the mailbox: [REDACTED]
[REDACTED] When the file is submitted to BMS, it must be noted whether the file contains all Non Serious Adverse Events (only adverse events not previously submitted to BMS within the 3 months).

6.5.2 Institutional Review Board (IRB) and Institutional Biosafety Committee (IBC)

All serious adverse events will be reported to the IRB and IBC per institutional guidelines. Upon receipt of the report of the serious adverse event by IRB and IBC, follow-up information will be given to the IRB and IBC within 15 days.

6.5.3 Food and Drug Administration (FDA)

All reporting to the FDA will be completed by the IND Sponsor.

6.5.3.1 Expedited IND Safety Reports

7 Calendar-Day Telephone or Fax Report:

The IND Sponsor is required to notify the FDA of any fatal or life-threatening adverse event that is unexpected and assessed by the investigator to be possibly related to the investigational agent. Such reports are to be telephoned or faxed [REDACTED] to the FDA within 7 calendar days of first learning of the event.

15 Calendar-Day Written Report:

The IND Sponsor is required to notify the FDA of any serious adverse event that is unexpected and possibly related to the investigational agent in a written IND Safety Report.

Written IND Safety Reports should include an Analysis of Similar Events in accordance with regulation 21 CFR § 312.32. All safety reports previously filed with the IND concerning similar events should be analyzed. The new report should contain comments on the significance of the new event in light of the previous, similar reports.

Written IND safety reports with Analysis of Similar Events are to be submitted to the FDA within 15 calendar days of first learning of the event.

6.5.3.2 IND Annual Reports

In accordance with the regulation 21 CFR § 312.33, the IND Sponsor shall within 60 days of the anniversary date that the IND went into effect submit a brief report of the adverse events and progress of the investigation. Please refer to Code of

Federal Regulations, 21 CFR § 312.33 for a list of the elements required for the annual report. All IND annual reports will be submitted to the FDA by the IND Sponsor-Investigator.

6.5.4 Recombinant DNA Advisory Committee (RAC)

Unexpected SAEs believed to be related to the investigational product(s) will be reported to RAC by email if fatal or life-threatening within 7 calendar days or by written report if related and unexpected to the investigational product(s) within 15 calendar days. SAEs that are unrelated or related and expected with the investigational product (s) will be reported to RAC in the Annual Report. Follow-up information will be submitted to the RAC as soon as relevant information is available.

7. PHARMACEUTICAL INFORMATION

7.1 GVAX Pancreas Vaccine

7.1.1 Agent Accountability

The IND Sponsor or the IND Sponsor's representative shall take responsibility for and shall take all steps to maintain appropriate records and ensure appropriate supply, storage, handling, distribution and usage of investigational product in accordance with the protocol and any applicable laws and regulations.

7.1.2 Mode of Action

GM-CSF-secreting, irradiated, whole cell vaccines recruit and activate tumor-specific T-cells and induce a cytotoxic response through two mechanisms: 1. they deliver a range of peptide antigens (without the need for specific knowledge of the relevant target antigens), and 2. GM-CSF is an important growth and differentiation factor for dendritic cells, which are potent antigen-presenting cells.

7.1.3 Description

GVAX pancreas vaccine, PANC 10.05 pcDNA-1/GM-Neo Clinical Lot (Irradiated) and PANC 6.03 pcDNA-1/GM-Neo Clinical Lot (Irradiated) is a white, milky suspension in a 2 ml cryovial. Each of the pancreatic tumor cell lines have been genetically-modified with a plasmid vector encoding the cDNA for human GM-CSF and subsequently cultured and irradiated.

The vaccine consists of equal numbers (2.5×10^8 each) of irradiated PANC 6.03 and PANC 10.05 cells combined into a single vaccination. Vaccine cells from each pancreas tumor cell line are frozen at 1.25×10^8 cells/vial (2 vials per cell line) in an injectable formulation of Hespan (6% hetastarch in 0.9% sodium chloride with 2% human serum albumin and 5% DMSO). The GVAX pancreas vaccine will be thawed on the day of vaccination and taken up into syringes.

A Phase I/II trial of combination immunotherapy with nivolumab and a CCR2/CCR5 dual antagonist (BMS-813160) with or without GVAX following chemotherapy and radiotherapy for locally advanced pancreatic ductal adenocarcinomas (PDACs)

7.1.4 Packaging and Labeling Information

Vial labels on each cell line will contain the cell line name, either PANC 10.05 pcDNA-1/GM-Neo Clinical Lot, (Irradiated) or PANC 6.03 pcDNA-1/GM-Neo Clinical Lot (Irradiated) along with: the lot number, cell concentration and volume, date of manufacture, vial number, storage conditions, IND caution statement and manufacturer.

7.1.5 Preparation

Detailed instructions on the preparation of GVAX pancreas vaccine for administration will be provided in the Pharmacy Manual.

7.1.6 Storage

PANC 10.05 pcDNA-1/GM-Neo Clinical Lot (Irradiated) and PANC 6.03 pcDNA-1/GM-Neo (Irradiated) must be stored in vapor phase liquid nitrogen, less than or equal to -135°C.

7.1.7 Stability

Once thawed, the GVAX pancreas vaccine must be administered to the subject within 3 hours.

7.1.8 Route of Administration

Six intradermal injections: 2 in the right thigh, 2 in the left thigh, and 2 in the non-dominant arm. If one of these limbs is contraindicated, the dominant arm may be used.

7.1.9 Subject Care Implications

There is a possible risk of anaphylaxis and should be administered in a setting where emergency treatment is available. Administration should be immediately discontinued and the appropriate therapy instituted if there is a serious allergic reaction. The subject must be observed in the clinic for at least 60 minutes after the first set of injections and 30 minutes after subsequent injections. If an anaphylactic reaction is suspected, this must be discussed with the IND Sponsor, Merck and the Principal Investigator before the subject is given another dose of vaccine.

The vaccine should not be administered to subjects with a known hypersensitivity to GM-CSF, DMSO, hetastarch, trypsin (porcine origin), or fetal bovine serum. Subjects allergic to corn can also be allergic to hetastarch. Precautions include hypersensitivity reactions and anaphylaxis. At 5-fold human doses, hetastarch is embryocidal in animals.

The vaccine should not be administered to pregnant or nursing women, to subjects with

A Phase I/II trial of combination immunotherapy with nivolumab and a CCR2/CCR5 dual antagonist (BMS-813160) with or without GVAX following chemotherapy and radiotherapy for locally advanced pancreatic ductal adenocarcinomas (PDACs)

active or untreated brain metastases, or to subjects with autoimmune disorders such as systemic lupus erythematosus, sarcoidosis, rheumatoid arthritis, glomerulonephritis, vasculitis, etc. It should not be administered to subjects who may be at increased risk for bleeding or infection from intradermal injections such as individuals who have coagulopathies or decreased bone marrow function.

[figure not shown]
[figure not shown]
Systemic corticosteroids and immunosuppressive therapy should be avoided as they may inhibit the effectiveness of the vaccine, however, intranasal, intra-articular or topical steroids are permitted. The interaction with other vaccines is unknown.

[figure not shown]
The vaccine should be used with caution in subjects with a history of cardiac arrhythmias, pericardial or pleural effusions, congestive heart failure, pulmonary infiltrates, or lung disease associated with hypoxia.

[figure not shown]
7.1.10 Returns and Reconciliation

[figure not shown]
The investigator is responsible for keeping accurate records of the clinical supplies, the amount dispensed to, and returned by the subjects and the amount remaining at the conclusion of the trial.

Upon completion or termination of the study, all unused and/or partially used investigational product will be destroyed at the site per institutional policy. It is the Investigator's responsibility to arrange for disposal of all empty containers, provided that procedures for proper disposal have been established according to applicable federal, state, local and institutional guidelines and procedures, and provided that appropriate records of disposal are kept.

8. CORRELATIVE/SPECIAL STUDIES

Sample collection, storage, and shipment instructions are provided in the Laboratory Manual.

8.1 Tumor Tissue Studies

4-6 core tumor biopsies will be collected during

- 1) initial study enrollment if adequate diagnostic biopsy is not available,
- 2) the scheduled endoscopy with fiducial placement and
- 3) after pre-surgical evaluation if the patient is not a surgical candidate.

The core biopsy specimens will be collected for both snap frozen specimens and FFPE slides. The core formalin samples will be placed in one FFPE tissue block.

Additional tissue will be collected during surgical resection/NanoKnife procedure if the patient is a surgical candidate. Resected PDAs will be archived for FFPE tissue slides, frozen sections and freshly isolated TILs. Detailed instructions for tissue collection, processing and shipment are provided in the procedures manual.

The patient may also have biopsies of metastases performed. Post-treatment biopsies will only be obtained if the tumor is thought to be reasonably safe to biopsy, and biopsies not obtained due to concerns for patient safety will not be considered deviations. Additional optional biopsies may be obtained later in the course of therapy. Archival tumor samples will also be collected for every patient (slides and/or blocks). Archival tumor samples will not be

A Phase I/II trial of combination immunotherapy with nivolumab and a CCR2/CCR5 dual antagonist (BMS-813160) with or without GVAX following chemotherapy and radiotherapy for locally advanced pancreatic ductal adenocarcinomas (PDACs)

collected if the biopsy was a fine needle aspiration.

These tissue samples will be banked for the evaluation of PD-L1/PD-1, their associated immune suppressive pathways and other immune activation pathways to assess the effect of treatment upon the tumor microenvironment and the correlations between these immune parameters and clinical response. Immunohistochemistry, flow cytometry, quantitative PCR assays and microarray analysis will be employed. In addition, to identify potential mutated neoepitope-specific T-cell repertoire by TCR clonality and/or the MANAFEST assay and in pre- and post-treatment tumor specimens and peripheral blood lymphocyte (PBL) over time on treatment.

8.2 Peripheral Blood Lymphocytes (PBLs) and Circulating Tumor Cells (CTC)

Whole blood of up to 100 mL will be collected as per the study calendar (Section 9) and used for PBL processing. During the Post-Immunotherapy Evaluation visit (Cycle 1 Day 28), additional plasma will be isolated from a portion of this sample (approximately 50 mL) while it is being processed for PBL to support the isolation of tumor infiltrating lymphocytes. Post-treatment expression of PD-1 and other lymphocyte activation markers will be measured and correlated with OS and MFS. PBL are isolated and stored frozen until use. PBL will be banked for measuring peripheral mesothelin-specific T-cell responses as an established parameter of immune response to treatment with GVAX. PBL will also be banked for an ELISPOT-based approach similar to the approach we used to define the mesothelin T-cell epitopes to validate mutant neoepitopes predicted for HLA-A1 and HLA-A2, including the HLA-A2-binding neoepitopes for the common Kras exon 12 mutations (KrasG12V and G12D).

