1.5.1 Efficacy Endpoints

- OS from the time of Cycle 1, Day 1 of immunotherapy until death from any cause.
- MFS from the time of Cycle 1, Day 1 of immunotherapy until first documented distant metastases on imaging or death, whichever occurs first.
- LPFS from the time of Cycle 1, Day 1 of immunotherapy until first documented local progression on imaging or death, whichever occurs first.
- Surgical resectability determined by successful performance of resection (as defined by R0 and R1 resection).
- Pathologic response as determined by surgical margins and residual disease.

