4.10 End of Treatment (EOT)

All subjects will return to the study site 30 days (± 7 days) after the last dose of study drug (or within 7 days prior to initiation of a new anti-cancer treatment, whichever comes first) for an EOT evaluation. Procedures and assessments performed at this visit and beyond should follow the respective guidelines described in **Sections 4.11 and 9** as appropriate.

A Phase I/II trial of combination immunotherapy with nivolumab and a CCR2/CCR5 dual antagonist (BMS-813160) with or without GVAX following chemotherapy and radiotherapy for locally advanced pancreatic ductal adenocarcinomas (PDACs)

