9. STUDY SCHEDULE

Patients will be evaluated and consented at the time of initial diagnosis of LAPC. Patients should meet all eligibility criteria and complete all screening procedures prior to starting SOC chemotherapy, however they can be enrolled up to one month after initiating SOC chemotherapy to allow for time to gather all records from outside institutions if necessary. Patients will then receive 8-16 14-day cycles of FOLFIRINOX-based chemotherapy, followed by SBRT between 2-4 weeks after completion of chemotherapy. Both chemotherapy and radiation therapy are standard therapies for LAPC, and will be administered off-trial. They will have another evaluation for eligibility to receive immunotherapy after completion SBRT at which point they will be randomized during Phase II and they will initiate Cycle 1 Day 1 of combination immunotherapy within 2 weeks of completion of SBRT. The patient will undergo Post-Immunotherapy Evaluation within one week after Cycle 1 Day 28.

Pre-surgical Study Schedule						
Procedure	Screening/ Baseline	Pre-Immunotherapy Screening (within 3 weeks prior to C1D1)	Cycle 1 Immunotherapy (within 2 weeks after completion of SBRT)			End of Cycle 1 (day before surgery or C1D28, whichever is earlier) ²⁴
			C1D1 ²	C1D2 ³	C1D15 ⁴	
Visit Window ¹ (days)			-	-	+3	-3/+14
Nivolumab (All patients)			X			
GVAX (Phase 1 and Arm B patients)				X		
BMS-813160 (All patients) ⁵			X	X	X	X
Eligibility criteria	X	X				
Randomization (Phase 2 only) ⁶		X				
Demographics	X					
Medical History ⁷	X	X				
Medications	X	X	X		X	X
Physical Exam ⁸	X	X	X			X
Vital Signs and pulse ox ⁹		X	X	X	X	X
Height ⁹		X				
Weight		X	X		X	X
Performance Status	X	X	X		X	X
EKG for PR, QRS and QTcF ¹⁰		X	X		X	X
Hematology profile ^{11, 12}	X	X	X		X	X
Chemistry profile ^{11, 13}	X	X	X		X	X
TSH ^{11, 14}		X	X			X
Serum/Urine Preg ^{11, 15}	X	X	X			
CA 19-9 ¹¹	X	X	X			X
Urinalysis and microscopic exam ^{11, 16}		X				
INR ¹¹		X				
HLA-Typing ¹¹			X			
Adverse event evaluation		X	X		X	X
Vaccine Site Assessment						X
PET-CT, CT, or MRI ¹⁷	X	X				X ¹⁸
Tumor measurements ¹⁷	X	X				X ¹⁸
Pathology Review	X	X				
Peripheral blood for research (up to 100cc) ¹⁹			X			X
Serum (20cc) ¹⁹			X			X
Plasma (20cc) ¹⁹			X			X
Archival Tissue ²⁰	X					
EUS Core Biopsy ¹⁹		X ²¹				X ²²
QoL Questionnaire ²³			X			X

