20. Archival tissue from non-study biopsies may be collected at any time throughout the study.
21. Biopsy (4-6 cores) will be done during endoscopy for fiducial placement (not tied to pre-immunotherapy screening visit timing).
22. EUS Guided biopsy will be obtained for research purposes if subject is not a surgical candidate. If subject is a surgical or NanoKnife candidate, biopsy will be obtained intraoperatively during surgical resection. If metastases are noted, subjects will be offered a biopsy of metastases for research purposes.
23. QOL survey may be completed up to 3 days prior to a visit.
24. If End of Cycle 1 window overlaps with C1 D15 window, these visits may be combined.

A Phase I/II trial of combination immunotherapy with nivolumab and a CCR2/CCR5 dual antagonist (BMS-813160) with or without GVAX following chemotherapy and radiotherapy for locally advanced pancreatic ductal adenocarcinomas (PDACs)

Surgery should be scheduled to occur between five to seven weeks after completion of SBRT. If surgery is scheduled after completion of Cycle 1 (i.e. >28 days from nivolumab dosing), anti-CCR2/5 (BMS-813160) therapy will be continued up to the day before surgery. A second dose of nivolumab and GVAX will not be administered because this is not considered a new cycle. Standard surgical procedure will be determined by the operating surgeon. The surgical procedure is considered standard of care, but must be performed at Johns Hopkins Hospital.

Post-treatment biospecimens will be obtained the following ways:

- Surgical candidate found to have resectable tumor – resected specimen will be obtained intraoperatively
- Surgical candidate found to have unresectable tumor – research core biopsies will be obtained intraoperatively
- Non-surgical candidate – EUS-guided tumor biopsy
 - Note, if a patient is noted to have developed metastases that can be safely biopsied (as determined by our interventional radiology team), they will be offered biopsy of the metastases.

For those who undergo a surgery or NanoKnife procedure, immunotherapy will be initiated within 6 to 12 weeks of the procedure. For those who are not surgical candidates, the immunotherapy will not be held.

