- To assess correlation between immune parameters and clinical outcomes using univariate and multivariate Cox regression models

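### The planned correlation of post-treatment immune markers with OS and MFS names neither the draw nor a clock that starts at it, so a late draw could make a marker that merely drifts look protective

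*Combined protocol and SAP*

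**What the plan says.** Section 8.2 plans the analysis in one sentence: "Post-treatment expression of PD-1 and other lymphocyte activation markers will be measured and correlated with OS and MFS". It takes the sampling times from the calendar: "Whole blood of up to 100 mL will be collected as per the study calendar (Section 9) and used for PBL processing". In Section 9, research blood is drawn at Cycle 1 Day 1, End of Cycle 1, Cycle 2 Day 1 and EOT. Patients who take maintenance have their EOT draw at the end of maintenance instead.

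The endpoints in 1.5.1 are "OS from the time of Cycle 1, Day 1 of immunotherapy until death from any cause" and "MFS from the time of Cycle 1, Day 1 of immunotherapy until first documented distant metastases on imaging or death, whichever occurs first".

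The method in 12.1 is "To assess correlation between immune parameters and clinical outcomes using univariate and multivariate Cox regression models". Section 12.8 repeats Cox regression for candidate biomarkers, takes all subjects as evaluable, and describes its aim as finding baseline biomarkers. It gives patterns over time to mixed models.

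Under 4.9, distant metastasis ends treatment. Under 4.10, the EOT visit falls 30 days (±7) after the last dose, or shortly before a new anti-cancer treatment if that is sooner.

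No section says which draw counts as post-treatment in 8.2. None sets a landmark, delayed entry or a time-dependent covariate.

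**The concern.** A Cox model with its clock at Cycle 1 Day 1 treats the covariate as known on that day. A post-treatment marker is known only later, and only in patients who live long enough to be sampled.

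That matters little if everyone is sampled at about the same early time. It matters more when the draw time is tied to the patient's course. Cycle 2 Day 1 is late in operated patients and early in the others. EOT is early in a patient who develops metastases on treatment and late in one who does not. In the first patient, the MFS event causes the sample that is meant to explain it.

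A marker that only changes with time or drug exposure would then differ between early and late failures without any link to the hazard. At stake is a misleading exploratory statement that immune activation goes with longer survival.

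**Working it through.** The plan gives no sample size, alpha or event count for this analysis, so there is no stated figure to reproduce. The check has three parts.

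**1. When the draws fall after Cycle 1 Day 1** (Sections 1.7, 4.1, 4.10 and 9; 52.18/12 = 4.348 weeks per month)

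- End of Cycle 1: Day 28, or the day before surgery if earlier, with a window of -3/+14 days. The last permitted day is 28 + 14 = Day 42.
- Surgery: 5 to 7 weeks after SBRT, with Cycle 1 starting 0 to 2 weeks after SBRT. That gives 5 - 2 = 3 to 7 - 0 = 7 weeks after Cycle 1 Day 1, so surgical tissue can be as late as about Day 49.
- Cycle 2 Day 1, operated: 6 to 12 weeks after surgery, so 3 + 6 = 9 to 7 + 12 = 19 weeks. Not operated: treatment is not held, so about week 4 to 5. Section 3.6 excludes patients with metastases on imaging from post-surgical treatment. An operated patient sampled here therefore carries 9 to 19 weeks of guaranteed metastasis-free time.
- EOT, dosing to the end of Cycle 5, not operated: 20 + 30/7 = 24.3 weeks = 5.6 months (the protocol says about 6). Operated: 25 to 35 weeks + 30/7 = 6.7 to 9.0 months (the protocol says 7 to 9). With 24 weeks of maintenance: 11.1 months if not operated, 12.3 to 14.6 if operated.

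**2. How often the MFS event comes first**

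Assume exponential times with the 7.7-month median MFS that Section 2.2 reports for an SBRT cohort: P(event by t) = 1 - 0.5^(t/7.7).

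- t = 5.6 months: 1 - 0.5^0.727 = 40%.
- t = 11.1 months: 1 - 0.5^1.442 = 63%.

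**3. False-positive rate for a marker with no effect, EOT draw**

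Assumptions, 3,000 trials per setting:

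- Time to metastasis: exponential, median 7.7 months.
- Survival after metastasis: exponential, median 13.9 - 7.7 = 6.2 months. Medians do not add, so simulated OS is somewhat longer than the 13.9 months in Section 2.2.
- 35% resected (Section 1.7: 30-40%). Maintenance uptake 50% (not in the documents). Administrative censoring at 36 months.
- Draw 30 days after the earlier of planned end and metastasis, in patients alive then.
- Marker = noise (SD 1) + drift × months to last dose.
- Cox score test from Cycle 1 Day 1, two-sided 5%.
- n = 15 (Phase II maximum) and n = 25 (both phases together allow 15 + 3 = 18 to 15 + 12 = 27 if Phase II fills).

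| Drift, SD/month | OS, n=15 | OS, n=25 | MFS, n=15 | MFS, n=25 | Median OS hazard ratio per unit (n=15, n=25) |
|---|---|---|---|---|---|
| 0 | 6.1% | 5.8% | 5.7% | 6.3% | 0.99, 0.99 |
| 0.05 | 6.2% | 6.1% | 7.7% | 7.7% | 0.91, 0.93 |
| 0.1 | 8.3% | 10.2% | 13.4% | 15.9% | 0.86, 0.85 |
| 0.2 | 15.5% | 21.5% | 28.1% | 38.7% | 0.79, 0.80 |
| 0.3 | 20.9% | 31.9% | 41.0% | 57.5% | 0.77, 0.78 |

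About 52% of EOT samples came after the MFS event.

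Comparators for OS: a marker drawn at End of Cycle 1 with the clock started at Day 28 gave 5.4% to 6.4% in every setting. The EOT draw with delayed entry at the draw gave 4.1% to 8.5%. The remaining excess at strong drift is expected, because an early EOT date itself signals metastasis.

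The Cycle 2 Day 1 draw was not simulated. Its problem rests on the timing in part 1.

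**The case against.** The strongest reply is that the documents never say the EOT sample will be correlated with survival. The sentence just before the planned correlation in 8.2 concerns the Cycle 1 Day 28 visit, and post-treatment tissue elsewhere means the specimen taken at surgery or surgical evaluation after Cycle 1. On that reading nearly everyone is sampled at a similar early time and the error stays near nominal. This stands: End of Cycle 1 is a natural reading. It is not a stated one, and the choice could be made after the data are seen.

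Section 12.8 also directs its predictive aim at baseline biomarkers, so a reader would go too far in inferring that nothing in the plan points to baseline markers. That aim does not cover 8.2, which says post-treatment.

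A reader might also infer a formal test with a stated null hypothesis, or a survival claim resting on it. The documents give no null, alpha or decision rule here. They call the work exploratory, and 12.8 asks for point and interval estimates.

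Finally, the inflation depends on an assumed drift; without drift it disappears. The plan expects markers to change, since it compares pre- and post-treatment values and models patterns over time, but it gives no size. The 7.7-month median comes from patients given gemcitabine and SBRT, a different induction regimen.

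**Conclusion.** The point holds as a gap in specification: the draw and the clock are both left open for a post-treatment marker analysed against endpoints that start at Cycle 1 Day 1. The bias is small if only End of Cycle 1 blood is used. If EOT blood is used and the marker drifts by 0.1 to 0.2 SD per month, the false-positive rate at a nominal 5% is about 8-22% for OS and 13-39% for MFS with 15 to 25 patients, and a rising marker looks protective. These rates rest on the assumed medians, 50% maintenance uptake and the drift itself.

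The documents do not support the stronger reading that the plan commits to using EOT markers as predictors of survival. The analysis is exploratory and the Phase II primary endpoint, a pre/post response rate in tissue, is untouched. This is a cheap improvement.

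**What to change.** Change the wording in 8.2, 12.1 and 12.8:

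1. Keep Cox models from Cycle 1 Day 1 for baseline markers.
2. Name End of Cycle 1 as the main post-treatment draw. For any post-treatment blood or tissue marker, count OS and MFS from the sample date, in patients alive and, for MFS, metastasis-free at that time. A common landmark is an alternative if it is no earlier than the last permitted sample date. Day 42 would serve End of Cycle 1 blood, but surgical tissue needs about Day 49. Entering the marker as a time-dependent covariate is also acceptable.
3. Report EOT markers descriptively. Do not use them as predictors of MFS, or of OS from Cycle 1 Day 1.

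No new samples, visits or patients are needed. The cost is that the few patients with an event before the sample or landmark drop out of these models.
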